6.2.5 Other analyses and considerations

Health-related quality of life and SOFA-scores will only be assessed in those alive at the time of measurement and no imputation will be performed for those not alive at the time of measurement.

Survival until 90 days will be presented graphically with Kaplan-Meier curves,¹²³ but will otherwise be analyzed as a binary outcome as described in section 6.2.2.

Adverse events and categorical outcomes will only be presented descriptively.

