5.3 Tertiary outcomes

We will include 90-day survival as a measure of long-term survival. 90 days were chosen since it is unlikely that later mortality will be directly linked to the cardiac arrest or the trial intervention. 90 days is also consistent with recommendations from the American Heart Association.⁷⁷

Health-related quality of life at 30 and 90 days will be assessed by the EQ-5D-5L questionnaire,⁸⁸ which is supported by the American Heart Association⁷⁷ as well as the COSCA-initiative⁸⁷. EQ-5D-5L is a generic approach with five items covering symptomatic, physical, psychological, and social consequences of a disease. It is preferred to HUI3 and SF-36 because it is free to use and requires a shorter interview. Assessment of health-related quality of life by telephone is valid and reliable.⁸⁹ EQ-5D-5L allows for potential future cost-effectiveness analyses and comparison to the background population.

During the same 90-day interview, we will reassess neurological outcome (mRS and CPC).

In addition to the above, we will collect outcome data on early cardiovascular function, laboratory values, organ failure, and hospital disposition.

To assess cardiovascular function and organ failure, we will calculate the Sequential Organ Failure Assessment (SOFA)-score⁹⁰ at 2, 24, 48 and 72 hours after the cardiac arrest in those alive. The SOFA score is a validated and widely used measure of organ failure assessing the respiratory, nervous, cardiovascular, hepatic, coagulation, and renal systems.⁹⁰ We will assess both the cardiovascular sub score as well as the overall SOFA score. The calculation of the SOFA score will be based on available clinical and laboratory data. Laboratory and clinical data closest to the given time point will be used. If a given component (e.g., bilirubin) is not available it will be assumed to be within normal ranges. If PaO₂ values are not available, they will be imputed using imputations based on SpO₂ values.^{91,92}

Laboratory values, including pH, standard bicarbonate, PaCO₂, potassium, calcium, sodium, and lactate from the first arterial (or venous) gas will be compared between groups.

Hospital disposition (e.g., home, rehabilitation, nursing home, hospice) will be defined at the time of discharge from an acute care hospital.

All outcomes recommended by the recent COSCA initiative (Core Outcome Set for Cardiac Arrest) are included in the present study.⁸⁷

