6. SAMPLE SIZE CALCULATION AND STATISTICAL ANALYSIS PLAN

6.1 Sample size calculation

The trial will be powered to the primary outcome of ROSC. From the VAM-IHCA trial, which had similar inclusion and exclusion criteria, the proportion of patients with ROSC in the placebo group was 33%.³⁴ Based on an absolute difference of 10% between the placebo and the bicarbonate group, we anticipate that 33% in the placebo group and 43% in the intervention group will obtain ROSC. This corresponds to a relative increase of 30%. With such estimates, an alpha of 0.05, and the use of the Fisher's Exact test, we will need a total of 778 patients to have 80% power to detect a statistically significant difference between groups. Given that the primary analysis will be adjusted for strong prognostic factors (see section 6.2.2 and 6.2.4), we will obtain additional power.^{115,116} The trial therefore has a minimum of 80% power.

We anticipate no loss to follow-up for the primary outcome (see section 6.2.7). Patients who withdraw consent and request deletion of data will not be replaced. Of note, no patients withdrew consent in our previous trials.^{34,54}

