6.2.3 Continuous outcomes

Continuous data will be presented as means with standard deviations (SD) or medians with first and third quartiles depending on the distribution of the data. Differences between groups in continuous outcomes are presented as mean differences with 95% confidence intervals obtained from a generalized linear model with robust errors with adjustment for prognostic variables (see section 6.2.4). If the data are severely non-normally distributed, other methods (e.g., transformation of the outcome, quantile regression, Hodges–Lehmann median difference) will be considered or the data will be presented descriptively.

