6.2.4 Adjustment for prognostic factors

To increase power, we will adjust all outcome comparisons for strong prognostic factors.^{115,116} These will include age, whether the cardiac arrest was witnessed, and the initial rhythm. Age will be included as a linear continuous variable¹²² and the initial rhythm (shockable [ventricular fibrillation or ventricular tachycardia] or non-shockable [asystole or pulseless electrical activity]) and witnessed status as binary variables. A recent meta-analysis found that these variables are strongly associated with survival after IHCA.²⁵ To confirm that these variables are also strongly correlated to ROSC and other relevant outcomes in the Danish setting, we performed multivariable logistic regression with age, witnessed status, and initial rhythm as the independent

variables and various outcomes as the dependent variable using data from the VAM-IHCA trial (n = 501).³⁴ As can be seen in Table 3, these variables were strongly associated with outcomes.

Variable	Odds ratio (95%CI)					
	ROSC	30-day survival	30-day favorable			
		So-day Survivar	outcome (mRS 0-3)			
Age (per 10-year increase)	0.88 (0.70, 0.95)	0.67 (0.54, 0.82)	0.63 (0.49, 0.81)			
Non-witnessed vs. witnessed	0.50 (0.32, 0.79)	0.18 (0.06, 0.60)	0.26 (0.06, 1.11)			
Non-shockable vs. shockable	0.46 (0.25, 0.83)	0.35 (0.17, 0.72)	0.31 (0.13, 0.75)			

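### SOFA, and EQ-5D-5L if analysed as a score, is compared by adjusted mean difference among survivors only, which is not a randomised comparison if bicarbonate raises ROSC or survival

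*Protocol*

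**What the plan says.** Section 5.3 schedules SOFA "at 2, 24, 48 and 72 hours after the cardiac arrest in those alive" and states that "Health-related quality of life at 30 and 90 days will be assessed by the EQ-5D-5L questionnaire". Section 6.2.5 sets the population for both: "Health-related quality of life and SOFA-scores will only be assessed in those alive at the time of measurement". For patients who have died by then, the same section rules out any substitute value: "no imputation will be performed for those not alive at the time of measurement".

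The effect measure comes from the general rule in section 6.2.3: "Differences between groups in continuous outcomes are presented as mean differences with 95% confidence intervals obtained from a generalized linear model". Section 6.2.4 applies covariate adjustment to every outcome comparison and names the covariates: "These will include age, whether the cardiac arrest was witnessed, and the initial rhythm".

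Four other provisions bear on the point.
- Section 6.2.5 reserves purely descriptive reporting for adverse events and categorical outcomes.
- Section 6.2.3 allows other methods, or description, for severely non-normal data.
- The multiple imputation in section 6.2.7 is for loss to follow-up, not for death.
- Section 6.2.1 says there will be no separate analysis plan, so the matter is not deferred elsewhere.

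**The concern.** Being alive at 2 to 72 hours, or at 30 or 90 days, happens after randomisation, and it is what the drug is meant to change. Section 2 hypothesises more ROSC and better 30-day survival on bicarbonate. Section 6.1 puts numbers on the first: "we anticipate that 33% in the placebo group and 43% in the intervention group will obtain ROSC". In that scenario the survivors in the bicarbonate arm are a mixture. Some would have lived under either treatment, and some live only because of bicarbonate. The second kind has no counterpart among the placebo survivors. If they are sicker, mean SOFA is higher and mean quality of life lower on bicarbonate, although no patient was made worse.

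Age, witnessed status and initial rhythm remove only the part of the imbalance that they explain. Section 1.1.3 names arrest duration as a main driver of poor outcome, and it is not in the model. It could not simply be added, because the treatment may itself shorten the arrest.

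At stake is how the tertiary results in the main publication are read. The protocol gives no estimand for survivors, no companion analysis that counts death, and no caution on interpretation.

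**Working it through.** **Inputs from the protocol.** ROSC 33% on placebo and 43% on bicarbonate; 778 patients, 1:1; two-sided alpha 0.05; 80% power; Fisher's exact test.

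**Inputs assumed, because the protocol does not give them.** The excess score d of the added survivors, the SDs, the mean SOFA, the EQ-5D index values and the survival rates. Ranges are shown.

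**The plan's own figure.** The continuity-corrected formula for 33% versus 43% gives 389 per arm, 778 in total. Exact Fisher power at 389 per arm is 80.2%. The sample size is reproduced, and this point does not affect it.

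**Share of added survivors.** Expected ROSC counts are 0.33 × 389 ≈ 128 and 0.43 × 389 ≈ 167. If every placebo-type ROSC would also occur on bicarbonate, the added patients are (43 − 33)/43 = 0.233 of the bicarbonate ROSC group.

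**Apparent SOFA shift.** Suppose bicarbonate has no effect on the score of patients who would survive under either treatment. Then

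shift = (pT − pC)/pT × d = 0.233 × d

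SE = SD × √(1/128 + 1/167), which is 0.35 for SD 3 and 0.47 for SD 4.

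The chance that the 95% CI lies wholly on the harm side is Φ(shift/SE − 1.96), against a nominal 2.5%:

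| d (points) | Shift | Chance, SD 3 | Chance, SD 4 |
|---|---|---|---|
| 1 | +0.23 | 10% | 7% |
| 2 | +0.47 | 26% | 17% |
| 3 | +0.70 | 51% | 32% |
| 4 | +0.93 | 75% | 51% |

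A simulation of 2,000 trials with SD 3.5 and robust standard errors agrees: mean shift +0.48 and 21% for d = 2; +0.92 and 57% for d = 4.

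**A milder model.** Let risk be a continuous normal variable with correlation ρ to SOFA, so that bicarbonate moves the survival threshold from 33% to 43%. The difference in mean risk between the two survivor groups is φ(z₀.₃₃)/0.33 − φ(z₀.₄₃)/0.43 = 1.097 − 0.913 = 0.184 SD. The SOFA shift is 0.184 × ρ × 4, which is 0.15 for ρ = 0.2, 0.29 for ρ = 0.4 and 0.44 for ρ = 0.6.

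**EQ-5D-5L, if an index is analysed.** With placebo survival assumed at 10% to 25%, the same relative gain of about 1.3 and d of 0.1 to 0.3, the apparent loss is 0.023 to 0.070. With SD 0.25 to 0.30, the chance of a CI wholly on the harm side is about 6% to 55%.

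**What counting death does.**
- SOFA, with death set to 24 and mean 9 in those who would survive either way. Placebo: 0.33 × 9 + 0.67 × 24 = 19.05. Bicarbonate: 0.33 × 9 + 0.10 × (9 + d) + 0.57 × 24 = 17.55 + 0.1d. The difference is −1.5 + 0.1d, or −1.4 to −1.1 for d of 1 to 4.
- EQ-5D, with death set to 0, survival 10% versus 13%, and index 0.7 for those who would survive either way and 0.5 for added survivors. Among survivors: (0.10 × 0.7 + 0.03 × 0.5)/0.13 − 0.7 = −0.046. In all patients: 0.085 − 0.070 = +0.015.

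In both examples the sign reverses.

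**The case against.** The strongest reply is that the plan already compares outcomes that count death, and ranks them higher. ROSC is primary, and 30-day survival and mRS are the key secondaries, with death scored as mRS 6. Ninety-day survival is analysed as a binary outcome, and mRS is repeated at 90 days. SOFA and EQ-5D-5L are tertiary and section 6.2.8 gives them no P values. In the scenario of concern, readers would see higher ROSC, and any survival gain, in the same paper. This stands, and it limits the weight of the point. It does not remove it, because unadjusted 95% CIs for the survivor contrast will still be shown.

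Second, a reader might infer that the protocol fixes a survivor-only mean difference for EQ-5D-5L. It does not. Section 5.3 describes a five-item questionnaire without saying whether the index, the VAS or the item levels are analysed. Item levels would be categorical and so only descriptive. The point is firm for SOFA and conditional for EQ-5D-5L.

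Third, the size rests on assumed values. Except at the top of the range, the shift is small against its SE: 0.47 is one SE at SD 4. The ROSC counts only approximate the numbers alive at each SOFA time point up to 72 hours. The sums ignore covariate adjustment, which would reduce the shift somewhat. They also assume no benefit in patients who would survive either way, although sections 1.1.4 and 1.2.1 postulate one. All of this stands. A real benefit would be partly masked by the same selection, so it does not make the contrast easier to interpret.

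Fourth, ranking death worst puts most patients in a tie at the bottom, since 67% and 57% are expected not to reach ROSC. The all-patient SOFA comparison would largely repeat ROSC and survival. That is a fair reason not to replace the survivor table.

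**Conclusion.** The concern holds in a limited form. For SOFA the protocol fixes an adjusted mean difference with 95% CI among those alive. If bicarbonate raises ROSC or survival, that is not a randomised comparison and can lean towards apparent harm. At the planned ROSC rates the shift is 0.233 × d: about +0.2 to +0.9 points for assumed d of 1 to 4, or about 0.15 to 0.44 under smoothly graded risk, and somewhat less after adjustment. The direction depends on the added survivors being sicker. If bicarbonate does not change ROSC or survival, this bias largely disappears.

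A reader might go further and conclude that the trial will report false harm, or that its main conclusion is at risk. The documents support neither: d and the SDs are not given, and the confirmatory outcomes count death. Nor is survivor-only reporting wrong as description. The fault lies in presenting the difference as a treatment comparison without qualification. This is a cheap improvement.

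**What to change.** In section 6.2.5, state that SOFA and EQ-5D-5L in those alive are presented descriptively by arm. Alternatively, state that any between-group difference is conditional on survival and is not a treatment effect.

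Where a between-group effect is reported, add a comparison in all analysed patients: the EQ-5D index with death counted as 0, and SOFA by a rank-based method with death ranked worst. Say whether the EQ-5D-5L index, VAS or item levels are analysed. The same wording should cover quality of life at six months and one year, which section 5.5 says will be analysed like the 90-day outcomes.

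The cost is protocol wording and a small amount of analysis. No new data are needed, since section 5.2.2 expects virtually complete survival follow-up. The drawback is that the all-patient measure is driven largely by mortality and overlaps with ROSC and survival, so the survivor-only table should stay beside it.

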6.2.6 Subgroup analyses

Subgroup analyses will be performed on both the absolute and relative scale using risk ratios and risk differences as described in section 6.2.2.¹²⁴ These analyses will not include adjustment for prognostic variables. The analyses will include five pre-defined subgroup analyses for the primary and key secondary outcomes according to 1) first documented rhythm, 2) whether the cardiac arrest was witnessed, 3) patient age, 4) time from cardiac arrest to first trial drug, and 5) known metabolic acidosis prior to the cardiac arrest. The first documented rhythm will be dichotomized as shockable or non-shockable. Patient age and time from cardiac arrest to first trial drug will be dichotomized by the median. As a secondary analysis, these variables will be treated as linear, continuous variables and the results illustrated graphically. Known metabolic acidosis prior to the cardiac will be defined as a pH < 7.35 and a base excess < -2 mmol/L based on the latest laboratory values prior to the cardiac arrest. Only blood samples taken within 6 hours of the cardiac arrest will be considered.

6.2.7 Missing data

Missing data will be reported in the relevant publications for all variables. We do not expect any missing data for the primary outcome or the key secondary outcomes. In our two recent trials including patients with IHCA and OHCA, respectively, we did not have any missing data on these outcomes.^{34,54} We do not expect missing data on the SOFA scores or adverse events. There might be some limited missing data for neurological outcomes and health-related quality of life at 90 days (and potentially at 30 days) due to loss to follow-up. Assuming that data are "missing at random", multiple imputation using known risk factors for outcomes after IHCA will be used to impute values for patients with missing data if missing data is substantial (> 5%). In case outcome data are missing on < 5% of patients, a complete case analysis will be performed.

We do not expect missing data for the variables included in the regression models (see section 6.2.4). If data are missing on any of these variables, we will consider imputation or removal of that specific variable from the regression models.

6.2.8 Null-hypothesis testing and multiple comparisons

Null-hypothesis significant testing (and corresponding P values) will be considered for the primary outcome and the two key secondary outcomes in a hierarchical and sequential fashion such that the subsequent outcome will only be tested for statistical significance if the previous outcome had a P value < 0.05 (considered statistically significant). If this is not the case, no P value or test of statistical significance will be provided for the next outcome.¹²⁵ The order of the outcomes will be: sustained ROSC, 30-day survival, and 30-day with a favorable neurological outcome. P values will not be provided for other outcomes. All P values will be two-sided.

All confidence intervals will have 95% coverage and will not be adjusted for multiplicity.

6.2.9 Statistical stopping criteria

Since the primary outcome is not mortality, there will be no formal stopping criteria for efficacy. There will be no predefined stopping criteria for futility since enrollment of the full cohort might allow for detection of efficacy in subgroups or in other outcomes even if the primary outcome is neutral. Furthermore, since bicarbonate is commonly used during IHCA⁵⁷, a neutral trial with an adequate sample size will still be an important finding. There will be no formal stopping criteria for safety (see section 10.2).

6.2.10 Secondary Bayesian analyses

We will perform secondary Bayesian analyses for the primary and key secondary outcomes in order to aid interpretation of the results.¹²⁶ Given the limited evidence on bicarbonate use during cardiac arrest, we will primarily use noninformative prior probability distributions and the results obtained from the trial to obtain posterior probability distributions for risk ratios. More skeptical, neutral, and optimistic prior probability distributions will also be used consistent with a recent trial by our group.⁵⁴ The posterior probability distributions will be illustrated graphically, and the probability that the true treatment effect is larger than or within various thresholds (e.g., risk ratio above 1.0) will be provided. Lastly, we will provide the median risk ratio and risk difference with 95% credibility intervals.

7. DATA COLLECTION AND MANAGEMENT

7.1 Data collection process

A trained research nurse or research assistants, along with the site investigators, will be responsible for data collection and entry. Very limited data will be obtained from the clinical cardiac arrest team in real-time using an electronic case report form that will be accessible through QR codes and URLs. This will include the patient identifier (i.e., Danish Civil Registration System-number ["CPR number"]), timing of the first adrenaline dose, timing of the first trial drug administration, the total doses of trial drug administered, and reasons for not providing all trial drugs if relevant. This, along with the telephone interviews for long-term follow-up, will be the only source data and all additional data will be obtained from the electronical medical records or DANARREST (see section 7.6) and will be based on measurements and assessments made by the clinical team. Data will be entered directly into the database software (see section 7.3).

7.2 Variables

7.2.1 Overview

All IHCA patients at the participating sites will be entered into a screening log. For those not randomized, a specific reason for non-inclusion/exclusion will be documented. All randomized patients who received the trial drug will be entered into the main database.

A detailed data dictionary that clearly defines all included variables will be created prior to patient enrollment. The data dictionary will provide the name of the variable (including the code used in the database), a detailed definition of the variable, categories for categorical variables, and units and ranges for continuous variables. The number of collected variables will be kept relatively small to limit resource use and data entry mistakes. The included variables largely include those outlined in the IHCA Utstein guidelines.¹²⁷ Below is provided a brief overview of the included variables but details are reserved for the data dictionary.

7.2.2 Pre-cardiac arrest characteristics

Trial related variables

Trial ID

Site

Receipt of trial medication

Time of trial drug administration

Doses of trial medication provided

Requirement for emergency unblinding

Inclusion criteria

Exclusion criteria

Date and time consent for data collection is obtained

Patient demographics and characteristics

Name

Unique patient identifier (Danish Civil Registration System-number ["CPR number"]),

Age

Sex

Height

Weight

Conditions/medications prior to the cardiac arrest

Co-morbidities (cardiac and non-cardiac)

Frailty index

Estimated mRS prior to current hospital admission

Reason for admission

Length of stay prior to the cardiac arrest

Previous IHCA during this admission

Laboratory values prior to the cardiac arrest

BIHCA Protocol – version 1.5 Page **45** of **84**

7.2.3 Cardiac arrest characteristics

Location and time

Location of the cardiac arrest

- Date and time of the cardiac arrest
- Interventions in place
 - Vasopressors
 - Mechanical ventilation
 - Intravenous access
 - Renal replacement therapy

Cardiac arrest variables prior to the intervention

Presumed cause of the cardiac arrest

Initial rhythm

Monitored

- Witnessed
- Time to first rhythm analysis

Cardiac arrest variables after the intervention

Date and time of the end of resuscitation (ROSC or termination without ROSC)

Use of open-label sodium bicarbonate

7.2.3 Post-cardiac arrest characteristics

Laboratory values within the first 24 hours

Targeted temperature management

Temperature at 6, 12, 18, 24, 48, and 72 hours

Cardiac catheterization, percutaneous coronary intervention, and coronary artery bypass grafting

Procedures related to neurological prognostication (e.g., EEG, imaging, biomarkers)

Use of intravenous bicarbonate

Renal replacement therapy

Adverse events (see section 5.4.3)

7.2.4 Outcomes ROSC SOFA scores at 2, 24, 48 and 72 hours Hospital disposition Survival at 30 days, 90 days, 6 months, and 1 year CPC score at 30 days, 90 days, 6 months, and 1 year mRS at 30 days, 90 days, 6 months, and 1 year EQ-5D-5L at 30 days, 90 days, 6 months, and 1 year

